8.2 Randomisation, blinding and treatment allocation

8.2.1 Randomisation

With each new IP entering the platform, the randomisation ratio will be adapted. The day of randomisation will be Day 0. Treatment initiation will be as close to Day 0 as possible, using methods that may include directly dispensing IP to participants, or couriering medications to participants who are recruited centrally.

Included patients will be allocated to either an IP arm or a control arm. Each IP has a matching placebo or comparator. For specific IPs Usual Care can be a control arm (specified in ISA). When there is more than one arm with matched placebos in the trial simultaneously, placebos will be pooled for the primary analysis. This means that allocation will be split equally between all active IP arms the participant is eligible for, and placebo. For example, if there are 2 IPs with matching placebo randomisation will be 1:1:1 (Active A):(Active B):(Placebo), and within Placebo allocation will be 1:1 (Placebo A):(Placebo B). Primary analysis for a particular IP will include all participants allocated to placebo who were eligible for the IP and randomised in the same time frame, i.e. concurrent and eligible placebo participants. Potential participants can be included if they are eligible to be randomised to at least one IP. The trial will start with three trial arm 1:1:1.

Participants will be randomised using a rapid, secure, web-based randomisation system using non-deterministic minimisation, with a random element. The minimisation factors will be age (<55/≥55 years), time since onset of symptoms (≤2/>2 days), and country (Belgium/France/Germany/Ireland/Poland/Spain/UK). The randomisation sequence will be saved electronically in a working environment with restricted access.

Participants randomised to a treatment arm will be allocated to an IP pack according to the randomisation number. This individual investigational product pack will be dispensed to participants once they are randomised.

8.2.2 Implementation

The Site Investigator will be responsible for enrolling participants into the study, randomising them, and assigning them to their given randomisation numbers.

8.2.3 Blinding

This is a patient, investigator, and sponsor-blinded study. Each IP has a matching placebo or comparator. Participants, investigators, and the Sponsor will remain blinded to the study treatment (IP, placebo or comparator) throughout the study, except for the person who is responsible for generating the randomisation sequence, and the person who needs to be unblinded in order to label the IP(s)/placebo etc. In case of a medical emergency that requires unblinding of the IP, the Site Investigator can unblind the participant in order to give optimal medical treatment.

In case there is a Usual Care only arm active, this part is not double-blind.

8.3 Study procedures

General procedures are listed in this section (see also **Table 1**). Potential additional procedures for specific IPs will be detailed in each ISA.

8.3.1 Baseline visit, allocation, and IP supply

Baseline visit

- Patients with symptoms suggestive of COVID-19 or COVID-like-illness will be pre-screened for eligibility, and will be fully informed about the study. Eligible patients will be requested to give informed consent prior to start of full screening and trial procedures.
- Checking inclusion and exclusion criteria
- The following information will be collected in the baseline CRF:

- Demographics
- o Lifestyle
- Relevant comorbidities at presentation
- Vaccination history
- Prior COVID-19
- Individual signs and symptoms at presentation
- Anthropometrics
- Clinical assessments taken (if inclusion is face-to-face)
- Usual Care provided
- Swab will be taken
- Participants will receive trial instructions
- Participants will be randomly allocated to IP or control group
- If allocated to IP/control product: product dispensing and instructions
- Diaries/questionnaires will be explained and in case of paper, handed over to participants. In case of serious doubt about a participant's ability to complete the online diary, a paper diary should be recommended.
- Collection of additional samples if the specific IP requires, and further specified in the ISA

Participant pack:

Participants will receive a participant pack, containing: the participant information sheet (PIS), the signed informed consent form, swab kits, instructions for the combined throat-nose self-swab and a paper diary (if applicable). If allocated to a study arm with a product, then participants will also receive an investigational product pack with the IP/control product, a participant card and instructions detailing how the study product should be administered and precautions and possible adverse drug reactions or discomforts.

Days of study product intake (if applicable):

IP intake, doses per day and for the number of days is indicated. The duration of IP/control product intake is dependent on the IP and will be described in the ISA.

8.3.2 Follow-up

For 28 days

- Daily diary:
 - Questions related to feeling recovered
 - o Questions related to return to usual activity
 - o Individual symptoms with severities
 - o (Serious) adverse events
 - Participant reported overall wellbeing
 - o IP intake
 - Other medication intake
 - o Impact of symptoms on daily activities
 - New cases in households of participants
- Weekly diary:
 - Health care utilization
 - Complications
- Swab will be (self-)taken on day 4, 7 and 14

Telephone call day 14 (+4) as end of treatment visit:

- Completion of diary
- Questions related to feeling recovered and return to usual daily activity
- IP intake
- Health care utilization
- (Serious) adverse events

Telephone call day 28 (+7) in case diary data capture is not complete to capture a minimal outcome dataset

- o Questions related to feeling recovered and return to usual daily activity
- o IP intake
- Health care utilization
- o (Serious) adverse events

Follow up 3 months

- Questions related to feeling recovered
- o Questions related to return to usual activity
- Questions related to longer-term consequences of COVID-19 or COVID-like-illness
- o Impact on daily activities
- o Participant reported overall wellbeing
- Healthcare utilization

Follow up 6 months

- Questions related to feeling recovered
- Questions related to return to usual activity
- Questions related to longer-term consequences of COVID-19 or COVID-like-illness
- Impact on daily activities
- Participant reported overall wellbeing
- Healthcare utilization

Unscheduled call:

In case a participant discontinues the study due to the occurrence of a (S)AE, potentially related to the IP, the Site Investigator or delegate contacts the participant by telephone. In case of an SAE, a SAE form will be completed.

Contact details will be collected from the participants at baseline, including mobile and/or home telephone numbers to enable the collection of follow-up data.

8.3.3 Sample collection for laboratory measurements

Virology sampling

For the analysis of aetiology, participants will have a combined pharyngeal/nasal swab taken at baseline. The swab will be placed in 1 ml universal transport media UTM. Samples can be transported using standard transfer systems to a local laboratory, ensuring adherence to country-specific requirements for transfer of samples and according to the ECRAID-Prime laboratory sampling and storage manual. Once at the local laboratory the samples will be stored at -70°C, before transportation to the central laboratory in Antwerp, Belgium. In case the local lab does not have immediate access to a -70°C freezer, samples can be stored at -20°C. In Antwerp, samples will be stored at -70°C.

The export of all samples to Belgium will be done in accordance with country-specific regulations. The participant's date of recruitment and participant ID number will be used as identifiers for the samples. Laboratory and trial team will have access to this information for the purposes of sample identification and tracking. The participant's responsible clinician will not be informed of the results of these swabs because the results will not affect patient treatment and are only for research purposes. Analysis may be some time after swabs were taken. Each participant's swabs will be analysed to identify the causative pathogen, which will be done by a polymerase chain reaction (PCR)-based analysis with a multiplex test detecting COVID-19 or a COVID-like-illness. Upon identification of SARS-CoV-2, the sample will undergo next-gen sequencing (either short read Illumina based or long-read sequencing) to characterise the viral variants and identify variants of concern (VOCs), and also to identify viral mutations impacting the studied treatments. Following analysis, the remaining samples will be stored in a biobank being hosted by the Antwerp laboratory for Ecraid and for ECRAID-Prime. Samples will **only** be biobanked when specific consent was given for this procedure. Samples will be biobanked for further research into infectious diseases (as explained in the PIS).

Viral clearance and impact on biomarkers of illness severity

A semi-quantitative PCR will be applied in order to be able to conclude on lower test positivity. Viral clearance for a specific target (irrespective of SARS-CoV-2 or any other viral target) means that the PCR is negative on day 4, 7 or 14, or that Ct values are above a threshold of 35.

The impact on biomarkers, for example illness severity or immunological response, is dependent on the specific IP. If this will be an outcome parameter, it will be specified in the ISA.

Viral mutations

Raw sequencing reads will undergo quality assessment using FastQC, followed by quality trimming with TrimGalore v. 0.6.7 (https://github.com/FelixKrueger/TrimGalore), and reference mapping against the SARS-CoV-2 genome (GenBank: NC_045512.2) using the CLC Genomics Workbench v.9.5.3 (Qiagen). Clade and lineage assignment will be performed for all SARS-CoV-2 consensus sequences using Nextclade v.2.2.0 (https://clades.nextstrain.org) and Pangolin v1.9 (4.0.6) (https://pangolin.cog-uk.io), respectively. SARS-CoV-2 genome sequencing will be considered successful if: i) the resulting genome sequence harbored < 15% ambiguous base calls (Ns) in the consensus sequence, and ii) was successfully classified by both Pangolin and NextClade. For detection of genetic variants, trimmed reads will be mapped against the SARS-CoV-2 genome (GenBank: NC_045512.2) using the CLC Genomics Workbench v.9.5.3 (Qiagen) with a length and a similarity fraction of 0.7 and 0.99, respectively.

Other sampling

Specific biological marker levels and immunological response are dependent on the IP, and will be specified in the ISA.

Table 1. Schedule of Assessments

| | Baseline and Start study | | Follow-up | | | |
|--|----------------------------------|--|--------------------------------|--------------------------------|----------|----------|
| | Day 0 Screening/Randomisation | Days 1-28 | Telephone call 14 (+4) days | Telephone call 28(+7) days⁴ | 3 months | 6 months |
| Informed consent | х | | | | | |
| Demographics | х | | | | | |
| Relevant comorbidities and medication | х | | | | | |
| Randomisation | х | | | | | |
| Anthropometrics, lifestyle parameters | х | | | | | |
| Clinical assessments | x ² | | | | | |
| Vaccination and COVID-19 history | х | | | | | |
| Usual Care provided | х | | | | | |
| Virology sampling (swab) | x ¹ | x ¹ | | | | |
| Dispensing study product | х | | | | | |
| Return to usual activity and recovered | | Daily | х | х | х | x |
| Symptoms with severities | х | Daily | | | | |
| Participant reported overall wellbeing | х | х | | | х | х |
| Impact on daily activities | | Daily | х | х | х | x |
| Household transmission | | Daily | | | | |
| IP intake | x ³ | Daily ³ | х | х | | |
| Health care utilization | | Weekly | х | х | | |
| Blood sample | | | If required, see ISA | | | |
| Long-term infection consequences | | | | | х | х |
| Interview for qualitative study (if invited) | | Approximately two weeks after the initial consultation | | | | |
| (S)AEs, if required see ISA | х | Daily | x | х | | |

¹ Virology sample will be taken on day 0, 4, 7 and 14 (if additional swabs are needed then this will be specified in the ISA) ² If inclusion is face-to-face

³ The duration of study product intake is dependent on the IP requirements and can start on Day 0 or Day 1.

⁴ In case data capture is not complete

8.4 Withdrawal of individual participants

Participants are free to withdraw from the study at any time for any reason if they wish to do so without any consequences to their health care.

A Site Investigator can decide to withdraw a participant from the trial at any time if the Site investigator considers it necessary for any reason including:

- Ineligibility (either arising during the trial or retrospectively)
- If participation in the study will be perceived as a major burden for the patient

The reason for withdrawal will be recorded in the CRF. Whenever feasible, the following information should be documented on the End of Study form:

- Date of last contact
- Date of last intake study product
- Date of early termination
- Primary reason for early termination

Data up to and after the time of withdrawal will be included in the analyses, if allowed by the participant if they withdraw consent.

For participants who withdraw from the study due to the occurrence of an SAE, appropriate follow-up will take place (if agreed by participant) until the SAE has abated, or until a stable situation has been reached, with findings being recorded in the SAE form. Medical care of the discontinued participant is to be arranged by and at discretion of the Site Investigator or delegate, if necessary.

8.5 Replacement of individual participants after withdrawal

Additional participants will be included to compensate for participants that withdraw (equal number); withdrawals due to adverse drug reactions or adverse events based on study procedures will not be replaced.

8.6 Discontinuation treatment of individual participants

A Site Investigator can decide to discontinue a participant from treatment at any time for safety reasons if the Site investigator considers further treatment is a health risk for the participant, at the supervising clinician's discretion. IP specific guidance for discontinuation of treatment will be specificied in the ISA.

Cessation of study IP is not considered withdrawal from the trial (see section 8.4 for description for participants who withdraw their consent).

For participants who discontinue treatment due to the occurrence of an SAE, appropriate follow-up will take place until the SAE has abated, or until a stable situation has been reached, with findings being recorded in the SAE form. Medical care of the participant is to be arranged by the Site Investigator or delegate, if necessary.

8.7 Premature termination of the study or arm

The Sponsor has the right to terminate the trial or a specific arm prematurely if there are any relevant medical or ethical concerns, or if completing the trial is no longer feasible. Premature termination of ECRAID-Prime may occur because of a Regulatory Authority decision or a change of the opinion of the Independent Ethics Committee (IEC). If such action is taken, the reasons for terminating the trial must be documented in detail and the Sponsor must inform the IECs and the Competent Authorities (CA) (for the Member States concerned through the Clinical Trial Information System (CTIS)) within 15 days or according to local regulations. All trial participants still in the treatment period at the time of termination shall undergo a final examination which must be documented. The Sponsor must be informed without delay if any Site Investigator has ethical concerns about continuation of the trial. Premature termination of a specific IP will be considered if:

- The risk-benefit balance for the participant changes markedly
- It is no longer ethical to continue treatment with the IP
- The Sponsor considers that the trial must be discontinued for safety reasons (e.g. on the advice of the Data Safety Monitoring Board (DSMB))
- An interim analysis or results of other research show that one of the IPs is superior or inferior to another
- It is no longer feasible to complete the trial (e.g. it is unlikely that sufficient participants can be recruited in the trial within the agreed time frame etc.)

The Sponsor decides on whether to discontinue the specific IP in consultation with the trial statistician, as applicable. As directed by the Sponsor, all trial materials must be collected and all CRFs completed to the greatest extent possible. All essential documents necessary for the Trial Master File as defined in GCP will be filed.

9. SAFETY REPORTING

(S)AEs will be collected from participant's daily diaries, calls to participants, face-to-face visits with site clinicians, and medical records, and can be reported spontaneously by the participant, by the coordinating team or clinician.

ECRAID-Prime will implement a risk-assessed and proportionate approach to safety monitoring. In line with the summary of product characteristic (SmPC) or IB, we will assess the risks and the safety profile for each IP, and detail the mitigation and monitoring procedures in the ISA. All safety procedures will be according to Sponsor's Standard Operating Procedure (SOP).

9.1 Temporary halt for reasons of participant safety

The Sponsor will suspend the study if there is sufficient ground that continuation of the study will jeopardise participants' health or safety. The Sponsor will submit the notification to all IECs and CAs without undue delay of a temporary halt but not later than in 15 days of the date of the temporary halt. It shall include the reasons for such action and specify follow-up measures. The study will be suspended pending a further positive decision by the accredited IECs and/or CAs, as per national regulations. The coordinating teams and investigators will take care that all participants are kept informed.

9.2 AEs, SAEs and SUSARs

9.2.1 Adverse events (AEs)

AEs will be recorded for a maximum of 28 days. AEs are defined as any undesirable experience, unrelated to the respiratory infection, occurring to a participant during the study, whether or not considered related to the IP. For each IP/control, all AEs reported by participants in a daily diary from the start of treatment for a 28-day period or during the end-of-treatment telephone call assessment at day 14 (window 14-18 days) after randomisation) will be recorded. AEs will be assessed by a registered/delegated clinician for causality and severity (definitions below).

The participant will be asked to rate the severity of symptoms related to the respiratory infection, which can also be adverse drug reactions (for example headache), in their daily diary. The severity of individual events and symptoms will be assessed over time by participants on the following scale: absent, mild, moderate, severe.

Respiratory symptoms and adverse drug reactions may overlap and can be difficult to disentangle. Trends in the prevalence in the severity of symptoms between control and IP arms will be compared, for evidence of increased severity of measured symptoms in those randomised to receive IPs.

Participants will be free to withdraw from taking the IP/control if they perceive an intolerable AE, unrelated to the respiratory infection. Participants will be provided with a participant card with a telephone number of the coordinating team, enabling them to report issues that are experienced whilst taking the drug. This card will also alert hospital clinicians about trial participation, should a participant be admitted to hospital. In the event of a medical emergency, trial participants will be instructed to show this card to the clinician they see. Based on clinical judgement, the medical monitor/study team may contact the participant to advise the participant on the appropriate clinical care.

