2.2 Secondary study objectives

The key secondary outcome will be early sustained recovery, which is defined recovery by day 14, sustained until day 28.

Other secondary objectives include assessment of the efficacy and safety of the study IP versus control on:

- Sustained recovery (participants' reported recovery that was maintained until 28 days)
- Time to first self-report of feeling recovered from individual symptoms of COVID-19 or COVID-like-illness (for Phase IIa type evaluation)
- Viral clearance (for Phase IIb and III type evaluation)
- Time to first self-report of return to usual daily activity
- Presence, duration and severity of individual respiratory symptoms
- Participant reported overall wellbeing
- Evaluation of overall safety of the IP by monitoring of (serious) adverse events and (serious) adverse drug reactions
- The use of additional antiviral medication
- The use of other prescribed and/or over-the-counter (OTC) medication for the RTI
- The occurrence of complications (hospitalisation, death; all-cause, non-elective hospitalisation will be assessed)
- Impact on usual daily activities
- Health care utilisation (e.g. general practitioner (GP) and hospital visits)
- Long-term (up to 6 months) consequences of COVID-19 or COVID-like-illness
- The incidence of COVID-19 and COVID-like-illness in other members of the household

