8. METHODS

8.1 Study parameters/ endpoints

- 8.1.1 Primary study endpoints (phase dependent) will be:
- Time to first self-report of feeling recovered from symptoms related to COVID-19 or COVID-like-illness (for Phase IIb/III type evaluation).
- Viral clearance and potentially impact on biomarkers of illness severity (for Phase IIa type evaluation, assessed at baseline and on days 4, 7 and 14 or specified in ISA if samples will be taken on other days).

8.1.2 Secondary study parameters/endpoints include:

Key secondary outcome: early sustained recovery (recovery by day 14 sustained until day 28). Other secondary endpoints:

- Sustained recovery (participants' reported recovery that was maintained until 28 days)

- Time to first self-report of feeling recovered from symptoms of COVID-19 or COVIDlike-illness (for Phase IIa type evaluation)
- Viral clearance (for Phase IIb/III type evaluation, assessed at baseline and on days 4,
 7 and 14 or specified in ISA if samples will be taken on other days).
- Time to first self-report of return to usual daily activity.
- Presence, duration, and severity of individual respiratory symptoms (runny/congested nose, sore throat, cough, fever shortness of breath, fatigue/tiredness, sweats/chills, headache, muscle, joint and/or body aches, loss of taste/smell, diarrhoea, nausea/vomiting, other) as: absent, mild, moderate, severe.
- Participant reported overall wellbeing, reported by rating of how well participant feels (scale 0-10).
- Overall safety of the IP by reporting (serious) adverse drug reactions.
- The use of additional antiviral medication (yes/no, name of medication)
- The use of other prescribed and/or OTC medication for the respiratory infection (antibiotics, antiviral medication, ibuprofen, other pain/fever medication, inhaled medication, intranasal medication, other).
- Impact on usual daily activities (work/education, caring for (grand-) children, household activities, sports, social life), as: no, slight, moderate, severe, not applicable.
- Complications (hospitalisation, death; all-cause, non-elective hospitalisation).
- Health care utilisation for COVID-19 or COVID-like-illness (GP and hospital visits).

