9.2.2 Adverse drug reactions (ADRs)

All adverse events judged by either the investigator/delegate or the Sponsor as having a reasonable suspected causal relationship to an IMP qualify as adverse drug reactions (ADR). An unexpected ADR is an ADR of which the nature or severity, outcome or frequency is not consistent with the applicable reference safety information for the IP.

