9.2.3 Serious adverse events (SAEs)

A serious adverse event is any untoward medical occurrence or effect that:

- results in death
- is life threatening (at the time of the event)
- requires hospitalisation or prolongation of existing inpatients' hospitalisation
- results in persistent or significant disability or incapacity
- is a congenital anomaly or birth defect
- is any other important medical event that did not result in any of the outcomes listed above due to medical or surgical intervention but could have been based upon appropriate judgement by the Site Investigator.

An elective hospital admission will not be considered as an SAE.

The Site Investigator or delegate will report all SAEs to the Sponsor without undue delay after obtaining knowledge of the events. Hospitalisations will be defined as at least one overnight stay. Hospitalisation for a pre-existing condition, including elective procedures planned prior to study entry, which has not worsened, does not constitute an SAE.

SAEs must be reported to the Sponsor by the person or nominated delegate who has discovered the SAE within 24 hours of becoming aware of the event. Some SAEs occurring within the 28-day follow-up period, may be identified retrospectively from diaries which will be received after 28 days. These will be reported within 24 hours of becoming aware of the event. The Sponsor or delegate will ensure SAEs being reviewed by the medical monitor for relatedness and expectedness as soon as possible, taking into account the reporting time for a potential suspected unexpected serious adverse reaction (SUSAR).

Procedure for immediate reporting of Serious Adverse Events

- The Study Site or national coordinating team will report all SAEs via the SAE form in the online data capture system 'Castor'. The study team at the Sponsor and the medical monitor will receive a notification about the SAE. GP, Study Site, national coordinating team will provide additional, missing or follow-up information in a timely fashion.
- If necessary, the participant may be contacted by GP practice to provide additional, missing or follow-up information as required.

A medical monitor will review the SAE once reported, collect information and report to the Sponsor within the SOP's timeframe. The Sponsor will submit an Annual Safety Report (ASR) including a list table of SAEs to all IECs and CAs of the participating countries (to all Member States concerned) through the CTIS once a year.

Expectedness

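### Defining adverse events as unrelated to the respiratory infection conflicts with the protocol's own ADR and SAE text, and leaves non-serious infection-related diagnoses treated at home without individual causality assessment

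*Protocol*

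**What the plan says.** Section 9.2.1 gives the definition: "AEs are defined as any undesirable experience, unrelated to the respiratory infection, occurring to a participant during the study". Clinician assessment of causality and severity is then prescribed for AEs.

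The same section adds that "The participant will be asked to rate the severity of symptoms related to the respiratory infection, which can also be adverse drug reactions", giving headache as its example. It concedes that "Respiratory symptoms and adverse drug reactions may overlap and can be difficult to disentangle", and plans a group-level safeguard: "Trends in the prevalence in the severity of symptoms between control and IP arms will be compared, for evidence of increased severity of measured symptoms".

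Section 9.2.2 builds ADRs from adverse events: those judged as "having a reasonable suspected causal relationship to an IMP qualify as adverse drug reactions".

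Section 9.2.3 opens with "A serious adverse event is any untoward medical occurrence or effect that" and lists the criteria for seriousness. They include other important medical events, so admission is not required. Relation to the infection is not a ground for exclusion.

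Complications are narrow in both places where they appear. Section 2.2 has "The occurrence of complications (hospitalisation, death; all-cause, non-elective hospitalisation will be assessed", and Section 8.1.2 has "Complications (hospitalisation, death; all-cause, non-elective hospitalisation".

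The safety endpoint depends on these definitions. Section 8.1.2 measures product safety by (serious) ADRs, Section 2.2 by (serious) AEs and ADRs, and Section 10 summarises AEs and SAEs by arm.

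**The concern.** The definition makes a judgement about cause a condition of entry. An event must be found unrelated to the infection before it counts as an AE, and only an AE can become an ADR. Elsewhere in the section the protocol says that this separation is hard to make.

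The first two products are nasal sprays, nitric oxide and saline, applied where many of these infections sit. Plausible local reactions, such as a congested nose, sore throat, cough or headache, overlap with the infection symptoms listed in Section 8.1.2. A product could also aggravate sinus, ear or airway disease without causing an admission. Such an event would naturally be put down to the infection, and it is the kind of event for which an individual look at causality is most useful.

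What is at stake is the coherence of the AE, ADR and SAE categories on which the safety endpoint rests, and whether individual non-serious infection-related diagnoses are assessed at all.

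**Working it through.** There is no stated figure to reproduce and no arithmetic applies. The check applies each definition literally to five kinds of event.

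| Event | AE (9.2.1) | ADR (9.2.2) | SAE (9.2.3) | Complication (2.2, 8.1.2) | Individual causality assessment |
|---|---|---|---|---|---|
| Non-serious, not attributed to the infection | Yes | Possible | No | No | Yes |
| Infection-related, unplanned overnight admission | No | No, read literally | Yes | Yes | Yes, as an SAE |
| Infection-related, important medical event without admission | No | No, read literally | Yes | No | Yes, as an SAE |
| Diary symptom (e.g. headache) attributed to the infection | No | 9.2.1 says it can be; 9.2.2 read literally says no | No | No | None prescribed; graded daily and compared by arm |
| Non-serious infection-related diagnosis treated at home (e.g. sinusitis, otitis, airway exacerbation) | No | No | No | No | None prescribed |

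Three results follow.

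1. **ADRs.** Section 9.2.1 allows an infection symptom to be a drug reaction. Section 9.2.2 takes ADRs only from AEs, and the AE definition shuts infection-related experiences out. The three statements cannot all hold.
2. **SAEs.** Rows two and three are SAEs but not AEs, so SAEs are not a subset of AEs.
3. **The gap.** The last row falls outside all four categories.

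The last row must then be set against everything else the protocol measures. Section 8.1.2 lists these secondary endpoints that could register such an event:

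- presence, duration and severity of individual symptoms, with an open item for other symptoms;
- overall wellbeing on a 0-10 scale;
- medication for the infection, including antibiotics and inhaled and intranasal products;
- GP and hospital visits for the illness;
- impact on daily activities.

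Time to first recovery and (early) sustained recovery also respond to worsening or relapse, and Section 9.2.1 compares symptom severity between arms. The event can therefore leave a trace in several places. None of them requires a diagnosis to be recorded, an AE entry to be made or a cause to be assigned.

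**The case against.** The strongest reply is that harm of this kind is still measured, and in a way that does not depend on attribution. The between-arm comparison of symptom severity is randomised and aimed at increased severity under the product. The endpoints on symptoms, wellbeing, medication, health care use and recovery add to it. This stands. A reader might infer that aggravation treated at home is captured by no safety or efficacy endpoint; the documents do not support that. The reply does not close the gap, however. The comparison is at group level and limited to measured symptoms, so harm in a minority can be masked where others improve, and no individual event is assessed.

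Other replies limit the point further:

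- **Serious events are not lost.** The SAE definition is the wider one, and every SAE is reviewed for relatedness. The mismatch with the AE definition is a matter of coherence.
- **The participant is not the only judge.** A reader might infer that the participant alone decides whether an event belongs to the infection. Section 9 also draws (S)AEs from calls, clinician visits and medical records. The definition excludes infection-related events whoever makes the attribution.
- **Differential attribution in open arms is limited.** Only Usual Care is open. Nitric oxide against saline is blinded, so this could affect only comparisons with Usual Care.
- **What the DSMB would see is unknown.** Section 9.7 says that it reviews safety data and leaves the details to a charter. One cannot say that a harmful product would look clean to the DSMB.
- **The appendices may add safety monitoring.** Section 9 sends product-specific procedures there. They are not shown. They could add detail, but the master definitions would still contradict each other.

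**Conclusion.** The point holds as a contradiction between definitions with one practical consequence. Sections 9.2.1, 9.2.2 and 9.2.3 do not fit together, and a non-serious infection-related diagnosis managed at home receives no AE entry and no individual causality assessment. Such events are visible only indirectly.

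The size cannot be given as a number. The protocol states no rate for such diagnoses, and Section 4.4 leaves sample size to the appendices. Any count per arm would rest on two assumptions, and would count all such events in an ill population, not the excess due to a product.

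The conclusion rests on a literal reading of the definitions and on the appendices not overriding them. Section 9.2.1 suggests that its authors did mean infection symptoms to be eligible as ADRs, in which case the definition does not say what was intended. This is an inexpensive improvement to safety ascertainment that also removes an inconsistency. It does not show that the trial would miss serious harm.

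**What to change.** Change Section 9.2.1 as follows:

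- Define an AE as any untoward medical event after randomisation, whether or not it is related to the infection or to the product.
- Exempt from separate AE entry only the named diary symptoms, which are already graded daily and compared between arms, unless the product is suspected as the cause.
- State that any new infection-related diagnosis is recorded as an AE and assessed for causality, with or without admission.

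ADRs and SAEs then both become true subsets of AEs. Section 9.2.2 can stay as it is, and the statement that infection symptoms can be drug reactions becomes consistent with it. The complications endpoint need not change.

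The cost is the wording change, a short addition to diary and CRF guidance, and somewhat more AE entries for clinicians to review. The exemption for diary symptoms limits that load. Because this is the master protocol, the new definition and guidance must be rolled out in all seven countries named in Section 8.2.1. The change concerns recording and assessment only, not how participants are treated.
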